A bootstrap sample (from a normal distribution with LSMeans and corresponding covariance matrix from an ANCOVA) is used to fit the non-linear dose-response functions and obtain parameter estimates for each model. Bootstrap model averaging based on AIC over all significant model families considered in the analysis will be used to estimate the final dose-response shape, to calculate the optimum dose(s) by substituting the values for the placebo-adjusted dose response in the model and solving for dose, and to derive the 95% confidence intervals. Bootstrap simulation will be performed using the multivariate normal distribution of the adjusted estimates of the population means for each dose and generalized least-squares fitting of the resulting

simulated values (Pinheiro et al 2014). The dose-response estimate will be the median across the bootstrap model predictions and 95% confidence intervals based on bootstrap quantiles.

The dose-response curve estimate with the model-based two-sided 95% confidence interval will be presented graphically. In addition, the plot will include the mean responses from the ANCOVA and the associated 95% confidence intervals for each of the studied dose groups.

Further details on the MCP-mod are described in [Section 5.7.1](#).

The target dose(s) will be estimated from MCP-mod for a delta of 0.36 and 0.68 based on the estimated dose-response curve (median of bootstrap estimates). The target dose is the smallest dose among the investigated doses which reaches the effect of delta..

The target dose(s) suggested by MCP-Mod based on viral endpoint serves as an important consideration in dose selection. However, the final dose selection for Part B will be determined based on the following

- Efficacy of doses based on rate of occurrence of hospitalizations (\geq 24 hours of acute care) and/or emergency room visits related to COVID 19 or death from any cause up to day 29, FDA/modified FDA symptom score; AND,
- Safety endpoints including [REDACTED] AESIs, AEs, and SAEs.

Part B

The primary objective of this Part is to demonstrate superiority of ensovibep, compared to placebo, in reducing the occurrence of hospitalizations (\geq 24 hours of acute care) and/or emergency room visits related to COVID 19 or death from any cause up to Day 29.

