5.7 Statistical models

5.7.1 Primary analysis

The following ANCOVA will be used for time-weighted change from baseline in \log_{10} SARS-CoV-2 viral load through Day 8:

Dependent variable = intercept + treatment + baseline in \log_{10} SARS-CoV-2 viral load + baseline risk for COVID-19 disease progression + presence of SARS-CoV-2 antibodies at baseline + geographic region + error.

The SAS procedure PROC MIXED will be used for analysis. Results will be presented with LSM and standard error (SE) for treatment effects and LSM, SE, associated two-sided 95% confidence interval, and two-sided p-value for treatment contrasts of each ensovibep dose versus Placebo.

- **MCP-Mod**

The Multiple Comparison Procedure – Modelling (MCP-Mod) methodology (see [Bretz et al 2005](#) and [Pinheiro et al 2014](#)) will be employed to assess the primary objective. The following steps for the MCP-Mod methodology will be performed. The analysis will be implemented in SAS (used for ANCOVA) and R (MCP-Mod) using DoseFinding R package:

Step 1 (Testing an overall dose-response signal - MCP part):

- a. Fit ANCOVA model. Extract estimates and variance-covariance matrix from fitted model.
- b. Perform multiple contrast test with pre-defined model types and optimal contrasts, using variance-covariance matrix from the ANCOVA.

Consider the following candidate models:

- Emax (ED50=8)
- Emax (ED50=40)
- Emax (ED50=180)
- sigEmax (ED50=120, h=4)
- sigEmax (ED50=450, h=3)

Present t-statistics and corresponding adjusted p-values for each candidate model.

If there is at least one significant DR relationship, the DR signal is declared and Step 2 will be performed.

Step 2 (Estimation of the dose-response curve and target dose – Mod part):

- a. Draw bootstrap samples (at least 1000) from a multivariate normal distributions $N(\mu, \sigma)$ with parameter μ and σ populated with the corresponding LSMeans and variance-covariance from the ANCOVA of step 1a. Fit each of the pre-defined models to the data of each sample. Select the model with the best fit based on generalized AIC and predict the dose-response curve with this model in each sample.
- b. Derive median and other quantiles for predicted response over the dose range from the bootstrap samples. This will result in an averaged model.

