- c. Estimate the target dose(s) for a delta of 0.3, 0.8, and 1.5 using inverse regression techniques using the best model for each of the bootstrap samples. If at least 50% of the target doses are within the investigated dose range the target dose will be derived as the median of the bootstrap samples, the 95% interval will be derived from the respective quantiles. For this derivation only target doses within the boundaries for the parameter are included (i.e. range of 0 – 1.5*maxdose for Emax and sigEmax, 0 – 2*maxdose for exponential).

• Multiple imputation for supplementary analysis

A treatment policy will be used to handle (1) post-treatment initiation of all antivirals (including convalescent serum, antiviral antibodies, and antiviral small molecules) and immunosuppressive medications; and, (2) post-treatment increase in dose of immunosuppressive medications, for the treatment or management of COVID-19, and a patient will be evaluated regardless of experiencing either of these intercurrent events.

A composite strategy will be used to handle (3) death from any cause and (4) COVID-19 related hospitalization. In the event a patient experiences death or COVID-19 related hospitalization, all values after the time of death/start of COVID-19 related hospitalization for change from

baseline in \log_{10} SARS-CoV-2 viral load will be set as the worst observed value based on observed values at each time point within each treatment arm independently.

All measurements in \log_{10} SARS-CoV-2 viral load missing for other reason than death or COVID-19 related hospitalization will be multiply imputed assuming patients in the ensovibep treatment arms behave as patients in the placebo arm, i.e. using jump-to-reference (J2R). Missing data of patients in the placebo treatment arm will be imputed using missing at random (MAR) assumption.

For supplemental analysis using multiple imputation the following imputation steps need to be performed for missing data.

Missing data will be imputed for the visits before deriving the time-weighted change from baseline. Imputations will be done for change from baseline \log_{10} SARS-CoV-2 viral load, not for the absolute value:

1. Impute missing data using MAR for patient in the placebo arm:

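### SAP 2.5.2 and SAP 5.7.1 Step 2c give two incompatible current rules for the Part A MCP-Mod target dose; Step 2c should be replaced by the 2.5.2 rule

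*SAP*

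**What the plan says.** SAP 2.5.2 (dose-finding step) states: "The target dose(s) will be estimated from MCP-mod for a delta of 0.36 and 0.68 based on the estimated dose-response curve", that curve being the median of the bootstrap estimates. It then adds: "The target dose is the smallest dose among the investigated doses which reaches the effect of delta". It also tells the reader: "Further details on the MCP-mod are described in" Section 5.7.1.

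SAP 5.7.1, MCP-Mod Step 2c, states: "Estimate the target dose(s) for a delta of 0.3, 0.8, and 1.5 using inverse regression techniques", applied to the best-fitting model in each bootstrap sample. A target dose is derived only if at least half of the solved doses fall inside the investigated range. It is then the median, with a 95% interval from the quantiles. "For this derivation only target doses within the boundaries for the parameter are included"; those bounds include "2*maxdose for exponential", although the five candidates in the same section are all Emax or sigmoid Emax.

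The sections also differ on which models enter the curve. SAP 2.5.2 has "Bootstrap model averaging based on AIC over all significant model families considered in the analysis"; Step 2a of 5.7.1 has "Fit each of the pre-defined models to the data of each sample". Protocol 12.4.2 averages over all families considered, without the restriction to significant ones, while the data-analysis row of the Protocol summary mentions statistically significant models.

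**The concern.** Both rules are body text of the same SAP version, for the same output. They share no delta and use different estimators, so 5.7.1 cannot be read as the detail of 2.5.2. The SAP gives no order of precedence, the protocol gives no numeric delta, and SAP Section 4 lists no change to protocol-specified analyses. SAP 2.5.4 does not list either rule as a supplementary analysis.

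Section 5.7.1 is where the software (SAS, and R with the DoseFinding package) is named, so a programmer is likely to work from it. A programmer following Step 2c and a reader following 2.5.2 can report different target doses from the same data. SAP 2.5.2 makes the target dose an important input to the Part B dose. The supportive Day 8 MCP-Mod in SAP 2.5.5 promises similar outputs, so the conflict carries over to it.

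**Working it through.** **1. The two rules side by side**

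| | SAP 2.5.2 | SAP 5.7.1 Step 2c |
|---|---|---|
| Deltas | 0.36, 0.68 | 0.3, 0.8, 1.5 |
| Read from | median bootstrap curve | best model in each draw, inverted |
| Answer | smallest of 75, 225, 600 mg reaching delta | median of solved doses (continuous) |
| Condition | none stated | at least 50% of doses in range |
| 95% interval for the dose | not clearly stated | from bootstrap quantiles |

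**2. Which is intended.** The SAP document history for Amendment 2 describes the median-curve rule with 0.36 and 0.68, gives avoiding a lean towards lower doses as one reason, and names only Section 2.5.2 as affected. I use the log only as evidence of intent; the conflict is between two current sections. SAP 3.1 uses effects of 0.36 and 0.68 for sample size, and none of Step 2c's deltas appears there. The log does not reprint the superseded rule, so calling Step 2c un-updated text remains an inference.

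**3. Reproducing the plan's power.** Inputs from SAP 3.1 and 5.7.1: 100 per arm, doses 0, 75, 225 and 600 mg, one-sided 10%, SD 1.0 to 1.2, five candidate shapes. Effects are written as positive reductions.
- Optimal contrast under equal allocation: c proportional to μ − mean(μ). Statistic T = Σ c·ȳ / (σ√(Σc²/n)). Reject if the largest T exceeds q, with q about 1.69.
- Minimum power over shapes, effect 0.36, SD 1.0 / 1.1 / 1.2: 90.04 / 85.19 / 80.22% (plan 90.03 / 85.25 / 80.25%).
- Effect 0.68: 99.99 / 99.92 / 99.73% (plan 99.98 / 99.92 / 99.73%).
- Pairwise cross-check, effect 0.36, SD 1.0: Φ(0.36/(1.0·√(2/100)) − 1.2816) = Φ(2.546 − 1.282) = 89.7%.

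**4. Two worked curves**, with Emax effect E(d) = Emax·d/(d+ED50) and inverse d = ED50·δ/(Emax − δ).
- ED50 = 8, effect 0.36 at 600 mg: Emax = 0.36·608/600 = 0.365. Effects at 75, 225 and 600 mg are 0.330, 0.352 and 0.360. The 2.5.2 rule gives 600 mg for 0.36. Step 2c for 0.3: 8·0.3/(0.3648 − 0.3) = 37 mg. Bootstrapping around this curve (SD 1.0) gave 600 mg and about 33 mg.
- ED50 = 40, effect 0.68 at 600 mg: Emax = 0.68·640/600 = 0.725. Effects are 0.473, 0.616 and 0.680. The 2.5.2 rule gives 75 mg for 0.36 and 600 mg for 0.68. Step 2c for 0.3: 40·0.3/(0.7253 − 0.3) = 28 mg (29 mg by bootstrap), which rounds up to the same 75 mg. For 0.8 and 1.5 no dose solves the equation, since both exceed Emax; by bootstrap, 20% and 0% of draws were in range.

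**5. Simulation.** Five shapes, two effects and three SDs; 2,500 trials per setting, of which 1,965 to 2,500 were signal-positive; 1,000 bootstrap draws per trial. Models were fitted by generalized least squares on a grid (assumed bounds: ED50 0.6 to 900 mg, h 0.5 to 10). I paired 0.36 with 0.3 and 0.68 with 0.8, and rounded the 5.7.1 dose up to a studied dose. Neither step is in the SAP. Ranges span the shapes, among signal-positive trials; Monte Carlo error is about 1 percentage point.

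| Deltas (2.5.2 / 5.7.1) | True effect | Different dose, SD 1.1 | SD 1.0 to 1.2 | Direction |
|---|---|---|---|---|
| 0.36 / 0.3 | 0.36 | 30% to 50% | 26% to 51% | 5.7.1 lower, including 14% to 21% where only it names a dose |
| 0.36 / 0.3 | 0.68 | 4% to 23% | 3% to 23% | 5.7.1 lower |
| 0.68 / 0.8 | 0.68 | 33% to 43% | 31% to 46% | 5.7.1 higher or none, including 30% to 35% where only 2.5.2 names a dose |
| 0.68 / 0.8 | 0.36 | 2% to 3% | 1% to 5% | both usually name none |

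Delta 1.5 gave no dose in any trial.

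Splitting the causes at SD 1.1:
- Delta alone (5.7.1 estimator fixed): 27% to 37% in row 1 and 33% to 44% in row 3.
- Estimator alone, delta 0.36: 2% to 20% at effect 0.36 and 0% to 4% at effect 0.68.
- Estimator alone, delta 0.68: 0% to 17% at effect 0.68 and 0% to 1% at effect 0.36.
- Model set: only one family is significant in 7% to 29% of signal-positive trials at effect 0.36, yet this changes the 2.5.2 dose in under 0.3%.

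**The case against.** The strongest reply is that the SAP resolves the matter itself: its history names the rule, the deltas and the reason, so this is an appendix step that missed an edit. That supports the direction of the fix but does not remove the conflict, because 2.5.2 sends the reader to the section holding the other rule.

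Four further points stand and limit the claim.
- **SAP 2.5.2 is not clean either.** Its model-averaging sentence still obtains an optimum dose by inverting the model at the target effect, and derives 95% intervals without saying of what. Replacing Step 2c alone would leave that in place.
- **The percentages compare different quantities.** A dose for 0.3 is not a rival estimate of the dose for 0.36. Rows 1 and 3 are near worst case, because the true effect equals the 2.5.2 delta.
- **The missing doses depend on the true effect.** A reader might infer that Step 2c can hardly ever name a dose for its upper deltas. In a smaller run (300 trials per shape, 500 draws, SD 1.1) it named one for 0.8 in 91% to 97% of trials at effect 1.0, and for 1.5 in 96% to 99% at effect 1.8. In the same run, 2.5.2 itself named none for 0.68 in 33% to 50% at effect 0.68.
- **The model-set wording has no clear winner.** A reader might infer that Step 2a should be cut to significant families. Protocol 12.4.2 points the other way, the Protocol summary is mixed, and the Amendment 2 entry on the target dose is silent.

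**Conclusion.** The inconsistency is real and wrong as written: one output, two current rules, with different deltas and estimators. SAP 2.5.2 is very probably the intended rule, so following Step 2c literally would give the wrong target dose. It should be corrected.

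For true effects of 0.36 or 0.68 at 600 mg, SD 1.1 and 100 per arm, the rules disagree in about 2% to 50% of signal-positive trials, mostly because of the deltas. These figures are illustrative: they depend on the assumed curves and on my pairing and rounding.

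A reader might infer that up to half of such trials would carry a wrong dose into Part B, or that the Part A test is compromised. The documents support neither. SAP 2.5.2 rests the final dose on clinical events, symptoms and safety as well, so only the viral-load input is affected. The contrast test, its one-sided 10% level and the stated power do not use the target-dose rule.

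**What to change.** Before the Part A primary database lock:
1. Replace SAP 5.7.1 Step 2c with the 2.5.2 rule: deltas 0.36 and 0.68, the placebo-adjusted median bootstrap curve, and the smallest of 75, 225 and 600 mg reaching delta.
2. Delete the bound for the exponential model.
3. Reword the solve-for-dose sentence in 2.5.2 to match, and state whether a 95% interval for the target dose is still reported.
4. As an added clarification, not now in 2.5.2, report 'no target dose' when no studied dose reaches delta.
5. Make the model-set wording in 2.5.2 and Step 2a agree, in whichever direction the sponsor intends, with Protocol 12.4.2 in view.

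The cost is one SAP paragraph replaced and a few sentences edited. It needs no extra data, patients or analyses, and leaves one derivation fewer to program.

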5.7.2 Key secondary analysis

Not applicable.

5.8 Rule of exclusion criteria of analysis sets

Table 5.8-1 Subject Classification

Analysis Set	PD ID that cause patients to be excluded	Non-PD criteria that cause patients to be excluded
SCR	NA	Not having ICF; Not having screening epoch disposition page
RAN	NA	Patients not being randomized.
FAS	NA	Not in RAN; Mistakenly randomized and no study drug taken
SS	NA	No study drug taken
PK analysis set	To be defined	Patients not having at least one available valid (i.e. not flagged for exclusion) PK concentration measurement No study drug taken.

6 Reference

CDER (2020a) US Department of Health and Human Services, Food and Drug Administration, Guidance for Industry: Assessing COVID-19-related symptoms in outpatient adult and adolescent subjects in clinical trials of drugs and biological products for COVID-19 prevention or treatment. Rockville, MD.

CDER (2020b) US Department of Health and Human Services, Food and Drug Administration, Guidance for Industry: COVID-19: Developing drugs and biological products for treatment or prevention. Rockville, MD.

EMA (2014) Qualification Opinion on MCP-Mod as an efficient statistical methodology for model-based design and analysis of Phase II dose finding studies under model uncertainty [http://www.ema.europa.eu/docs/en_GB/document_library/Regulatory_and_procedural_guide/2014/02/WC500161027.pdf].

FDA (2016) Fit-for-purpose determination letter, [<https://www.fda.gov/downloads/Drugs/DevelopmentApprovalProcess/UCM508700.pdf>].

Kenward, M. G., & Roger, J. H. (1997). Small sample inference for fixed effects from restricted maximum likelihood. *Biometrics*, 983-997.
